1. BACKGROUND AND RATIONALE

The annual incidence of SCI in the United States is about 17,810 new cases; cervical lesions resulting in complete or incomplete tetraplegia account for 55% of new cases.¹⁻² In the acute phase after SCI up to 74-84% of people will experience respiratory complications such as pneumonia, atelectasis and ventilatory failure necessitating mechanical ventilation (MV).¹⁻³⁻⁹

Pneumonia is the leading cause of death after acute spinal cord injury (SCI) and is associated with poor neurologic recovery, increased length of stay, and increased mortality.¹⁻¹⁰⁻¹³ The impact of infection can be seen with decreased functional gains during acute rehabilitation.¹⁴ Therefore, strategies to mitigate the risk of pneumonia and facilitate early ventilator weaning **are of primary importance** to decrease morbidity and mortality and improve lifelong functional outcomes in people with SCI.

Optimal ventilator settings have been shown to reduce pneumonia and facilitate early weaning in people without SCI.¹⁵⁻²³ The ventilator settings of interest are tidal volume (Vt) and positive end-expiratory pressure (PEEP). Vt is the volume of air the ventilator provides with each “breath” in volume control modes. PEEP is the alveolar pressure above atmospheric pressure that is applied at the end of expiration to prevent cyclic opening and closing of alveoli to maintain adequate oxygenation.²⁴

Acute Respiratory Distress Syndrome (ARDS) Network protocol recommends smaller tidal volume ≤ 6 ml/kg predicted body weight (pbw) and positive end-expiratory pressure (PEEP) to prevent secondary respiratory complications and decrease mortality in people with ARDS, based on robust evidence from multicentre clinical trials.^{15 16 23} Following the ARDS Network trial, there have been several randomized clinical trials (RCTs) conducted in other diagnoses (non-ARDS and non-SCI population) in which Vt of greater than 8-12 ml/ kg pbw and less than 6-8 ml/kg pbw were compared.¹⁷⁻²² Results from these trials revealed a decreased risk of acute lung injury (ALI) and pneumonia in low Vt groups compared to high Vt groups.¹⁷⁻²²

However, current SCI clinical practice guidelines recommend starting Vt of 15 ml/kg pbw with an incremental increase in Vt up to 25 ml/kg pbw and weaning off PEEP.⁴ Unlike the needs for MV with pulmonary disease, respiratory function after SCI is limited by low lung volumes due to hypoventilation secondary to weakness or paralysis of inspiratory muscles. Therefore, bigger “breaths” (high Vt) are recommended to prevent atelectasis and improve lung capacity. In preparation for ventilator weaning, Vt is further increased.^{4 25} However, in studies comparing high vs. low Vt in non-SCI population, low Vt was not associated with a higher risk of atelectasis.^{17 20 21} Importantly, in our cohort study of people with acute SCI, we did not find any difference in improvement in breathing capacity or vital capacity with high Vt and moderate Vt MV.²⁶ Furthermore, emerging evidence in people with and without SCI suggests that low Vt leads to improved respiratory outcomes.^{17-22 26 27}

The presumed mechanism for worsening morbidity with increased Vt ventilation has been called **volutrauma**- overstretched alveoli leading to disruption of pulmonary epithelium and endothelium, lung inflammation, hypoxemia, and the release of inflammatory mediators which play a role in the development of pneumonia, lung injury, and sepsis.^{28 29} These changes result in poor pulmonary outcomes such as the prolonged need for mechanical ventilation, and increased risk for pneumonia.^{15 17-20 30} In human RCTs with and without ARDS, lower tidal volume ventilation resulted in a greater reduction of inflammatory markers, e.g., tumor necrosis factor (TNF) α , IL-6 compared to the higher tidal volume group.^{15 30-33} Current evidence in SCI supporting high Vt practice has several limitations.^{25 34} Current guidelines were written based on a small (n=42) retrospective study³⁴ in which vast range of Vts of 11.6 to 19.4 ml/kg ideal body weight (IBW) versus 20.3 to 32.2 ml/kg IBW were compared. The groups were different at baseline, with the low Vt group having a lower vital capacity at

admission and other factors suggesting a higher severity of SCI and respiratory impairment. This was not taken into consideration during the analysis. Further support for high Vt ventilation in SCI comes from a small randomized control trial (n=33) in subacute SCI comparing Vts of 10 and 20 ml/kg PBW, which did not find a difference in the rate of ventilator-associated pneumonia (VAP) and ventilator weaning days between 2 groups.²⁵ This study was limited by an underpowered sample size.²⁵ Therefore, the results of this study should be interpreted with caution.

Besides, preliminary results from our cohort studies and survey suggest:

- HVt in the ICU setting with increased probability of ventilator associate pneumonia (VAP).²⁷
- HVt in acute rehab is associated with a higher risk of pneumonia and pulmonary adverse event compared to moderate Vt.²⁶
- Variation in ventilator settings used for patients with acute SCI in acute care hospital at the time of discharge to a rehabilitation facility (Unpublished data).
- Variation in ventilator settings used in acute care hospital and rehabilitation facilities across the globe for patients with acute SCI (in press).

This clinically important controversy in acute SCI should be addressed in a large RCT with robust power analysis. However, prior to initiating a full-scale randomized clinical trial, a pilot comparative effectiveness randomized clinical trial is required to evaluate the outcomes and feasibility of recruitment, randomization, retention, and protocol adherence to demonstrate that the methods and procedures can work in a large-scale study. This pilot study will also help us identify inflammatory markers pertaining to lung injury in people with SCI.

2. HYPOTHESIS AND OBJECTIVES

We propose a pilot randomized comparative effectiveness trial comparing respiratory complications and inflammatory markers based on MV settings of 8-10 ml/kg pbw and higher Vt of 14-16 ml/kg pbw in people with acute cervical SCI in an acute inpatient rehabilitation hospital. Our **long-term goal** is to study optimal ventilator settings and treatment approaches in acute SCI to reduce infections and improve lifelong outcomes.

Objectives:

Objective 1: To compare MV outcomes of high vs. low Vt on the relative risk of pneumonia in the acute rehabilitation hospital.

Objective 2: To generate the feasibility data to inform the future RCT design. To achieve this objective, we will obtain the following data: a) Recruitment rate: the proportion of eligible people who provide consent (b) Adherence rate: the proportion of participants in each group who receive assigned intervention per protocol; (c) Retention rate: the proportion of participants in each group who complete all study procedures prior to discharge from our hospital; d) Missing data: Percentage of missing data in each group.

Objective 3: To analyze MV related lung injury inflammatory biomarkers in relation to tidal volume and outcomes.

Hypothesis:

Hypothesis 1: We hypothesize that Bayesian analysis will indicate a>70% probability of lower risk of pneumonia in people with acute cervical SCI receiving lower Vt MV than higher Vt.

Hypothesis 2: We hypothesize that we will be able to recruit **at least** 80% of eligible people each year and among recruited subjects, adherence and retention rate will be 80%, with less than 10% missing data on outcome measures.

Hypothesis 3.1: We hypothesize that MV-related lung injury inflammatory biomarkers (IL-1, IL6, IL-8, and tissue necrosis factor α levels) in serum and tracheal aspirate would be lower in the low Vt MV group compared to high Vt.

Hypothesis 3.2: People with acute cervical SCI receiving MV will have higher inflammatory markers levels than people with acute cervical SCI who do not require mechanical ventilation.

Hypothesis 3.3: People with acute cervical SCI independent of mechanical ventilation status who have higher inflammatory marker levels are more likely to develop pneumonia and other respiratory complications.

Potential Risks and Benefits:

The overall risk of pulmonary complications in people with acute SCI ranges from 74-84%. The proposed study is comparing tidal volume parameters used within current clinical practice. Our objective is to find optimal ventilator settings within the current clinical range to lower the current risk of pneumonia. Based on current evidence, pneumonia is associated with poor neurological recovery. Therefore, any decrease in the incidence of pneumonia can contribute to improved neurological recovery. There are no known risks of pulmonary complications due to participation in this study.

Risks of a blood draw and tracheal aspirate sample collection: The risks and discomfort of drawing blood include temporary discomfort from the needle stick, the possibility of pain or bruising at the blood draw site. Similarly, tracheal sample collection can also result in temporary discomfort.

Other Risks: There is a risk that confidentiality will be inadvertently compromised.

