9. SAFETY MEASUREMENTS

Collecting, Recording and Reporting of Adverse Events

An adverse event is any unfavorable and unintended sign, symptom, or disease temporally associated with the use of medical treatment or procedure that may or may not be considered related to the medical treatment or procedure.

Outcomes of this comparative effectiveness trial include data collection of adverse events. Adverse events include pneumonia and other ventilator-associated events, including acute care transfers due to respiratory complications, pneumothorax, transfer to acute care hospital due to respiratory complications, weaning failure, new pneumothorax, acute respiratory distress syndrome, pleural effusion, pulmonary embolism, atelectasis, and pulmonary edema.

The Investigators/ RA will be responsible for collecting and reporting adverse events during the trial. The investigators/ RA will collect adverse events related to the randomized control trial.

The PI will report problems according to the UTHSC-Houston IRB policy, specifically in the event which in the opinion of the PI is both unexpected and related and places subjects or others at risk of harm.

An adverse event is any unfavorable and unintended sign, symptom, or disease temporally associated with the use of medical treatment or procedure that may or may not be considered related to the medical treatment or procedure.

Outcomes of this comparative effectiveness trial include data collection of adverse events. Adverse events include pneumonia and other ventilator-associated events, including acute care transfers due to respiratory complications, pneumothorax, transfer to acute care hospital due to respiratory complications, weaning failure, new pneumothorax, acute respiratory distress syndrome, pleural effusion, pulmonary embolism, atelectasis, and pulmonary edema.

The Investigators/ RA will be responsible for collecting and reporting adverse events during the trial. The investigators/ RA will collect adverse events related to the randomized control trial.

The PI will report problems according to the UTHSC-Houston IRB policy, specifically in the event which in the opinion of the PI is both unexpected and related and places subjects or others at risk of harm.

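### The risk section's statement of no known pulmonary risk from participation is not supported by the protocol's own evidence on high tidal volume, and the 50% review does not ask for pulmonary events by ventilator arm

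*Combined protocol and SAP*

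**What the plan says.** Under Potential Risks and Benefits (Section 2), the protocol gives a high background risk ("The overall risk of pulmonary complications in people with acute SCI ranges from 74-84" per cent), notes that "The proposed study is comparing tidal volume parameters used within current clinical practice", and concludes: "There are no known risks of pulmonary complications due to participation in this study". The only risks it then lists are those of blood draw, tracheal sampling and loss of confidentiality.

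Section 1 reads differently. After describing overstretched alveoli as the presumed mechanism of harm from larger volumes, it says: "These changes result in poor pulmonary outcomes such as the prolonged need for mechanical ventilation, and increased risk for pneumonia". Of the investigators' rehabilitation cohort it reports: "HVt in acute rehab is associated with a higher risk of pneumonia and pulmonary adverse event compared to moderate Vt". It also cites an intensive-care cohort in which high Vt went with a greater probability of ventilator-associated pneumonia. Hypothesis 1 (Section 2) expects "a>70% probability of lower risk of pneumonia in people with acute cervical SCI receiving lower Vt MV than higher Vt".

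Section 9 names pneumonia and a series of other pulmonary events as adverse events. Its Safety Monitoring Plan has one statistical review at 50% recruitment. That review compares morbidity in study participants with controls, and its stopping criterion refers to pneumonia in one group against another.

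**The concern.** A suspected pulmonary harm of one assigned setting is the reason for the trial, yet the section that describes risk says that none is known. Participation matters here because it replaces the clinician's choice of Vt with random assignment. Potential participants have one day to decide (Sections 6 and 12), and many will need a third party to attest their consent, so the risk text from which a consent form would be written should be accurate.

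The same gap reaches the interim review. If pulmonary harm differs by Vt, the informative comparison is between the two ventilated arms and across all the listed pulmonary events. The review as written specifies neither, apart from the pneumonia criterion.

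**Working it through.** The plan gives no figure to reproduce, because the rehabilitation and intensive-care cohorts are cited without event rates, effect sizes or Vt cut-offs. The check is a comparison of sections, with simple arithmetic for scale.

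**1. Does the statement fit the stated evidence?** Section 2 denies known pulmonary risk from participation. Section 1 gives a presumed mechanism and two cohort associations in the direction of harm from high Vt. Section 2 turns this into a directional hypothesis. Section 6 says that the arm thresholds draw on the same rehabilitation cohort and on a survey. The evidence is preliminary, but it is known to the investigators and concerns an assigned setting.

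**2. Does usual care rescue the statement?** The statement could mean no risk beyond usual care. Section 8 gives the comparison for one centre:

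| | Vt, ml/kg pbw | PEEP |
|---|---|---|
| On arrival, median (IQR) | 7.5 (6.7-8.5) | 84% of patients |
| Usual in rehabilitation, median (IQR) | 14 (13-16) | withdrawn in all patients over the first day or two |
| High arm (Section 6) | 14-16 | 5-10 cm H₂O |
| Low arm (Section 6) | 8-10 | 5-10 cm H₂O |

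- The high arm lies inside the usual interquartile range for Vt, but is combined with PEEP, which that centre's data describe as withdrawn.
- The low arm lies below the usual interquartile range: 13 − 10 = 3 ml/kg pbw separates its upper limit from the lower quartile.
- Relative to the arrival median, the high arm is 14/7.5 = 1.87 to 16/7.5 = 2.13 times, and the low arm 8/7.5 = 1.07 to 10/7.5 = 1.33 times.
- Usual Vt at the second site is not given.

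The usual-care reading therefore covers the high arm's Vt at one centre. It does not cover both arms as specified at both sites.

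**3. Is there a pulmonary question for the low arm too?** Sections 1 and 8 say that larger volumes are used in spinal cord injury to prevent atelectasis, which Section 9 lists as an adverse event. The reassurance in Section 1 that low Vt does not raise atelectasis comes from patients without spinal cord injury. The risk section mentions neither point.

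**4. How many participants?** All 30 ventilated participants have their range set by allocation, 15 to each arm (Section 3). If the background range of 74-84% applied to the rehabilitation stay, 15 × 0.74 = 11.1 to 15 × 0.84 = 12.6 participants per arm would have a pulmonary complication. Section 1 gives that range for the acute phase, so carrying it over is an assumption. It does not measure any added risk.

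**5. What will the 50% review show?** Halfway through the ventilated cohort there would be 30/2 = 15 participants, or about 15/2 = 7.5 per arm. In Sections 3 and 5, controls means people not dependent on ventilation. Read that way, the morbidity comparison sets participants against a group that received neither Vt. Only the pneumonia criterion compares one group with another, and the other listed events have no stated comparison by Vt arm.

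**The case against.** The strongest reply is that both ranges are in current use, that the high arm is close to what one centre already does, and that cited guidelines start at 15 ml/kg pbw and go up to 25. The harm evidence is also weak: the cohort results are called preliminary, the mechanism is called presumed, and a small randomised trial (n=33, described as underpowered) found no difference in ventilator-associated pneumonia. Equating the cohort's high-Vt group with the 14-16 arm is an inference. All of this stands. It makes the added risk uncertain, but uncertain risk is not the same as no known risk.

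Three stronger readings are tempting and are not supported.

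- A reader might infer that the ethics-board reporting rule has no consistent answer for pulmonary events. The rule covers a problem that "in the opinion of the PI is both unexpected and related" and places someone at risk of harm. The high background risk and the list in Section 9 both support treating these events as expected, and the risk statement taken literally makes them unrelated. Either way they fall outside the rule. Criteria for expectedness and relatedness are not spelled out, but that is missing detail, and the governing board policy is not in the documents.
- A reader might infer that the pneumonia look is the only other safeguard. It is not. The protocol excludes ARDS and severe lung disease, allows discontinuation of the intervention for intolerance (Section 3), monitors airway pressures and provides medical consultation (Section 6), and has a desaturation procedure, adverse-event recording and a general morbidity review (Section 9).
- A reader might infer that participants are being misinformed. The consent pages are not available here. Section 6 provides separate forms because risks differ, Section 12 promises full disclosure, and the ethics board had the whole protocol.

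**Conclusion.** The concern holds in a limited form. The statement of no known pulmonary risk conflicts with Section 1 and with Hypothesis 1, and the usual-care explanation answers it only in part. It affects all 30 ventilated participants, since each has a range fixed by chance; the cited harm evidence concerns the 15 assigned to high Vt. The size of any added risk cannot be computed from the documents. The conclusion assumes that the cohort's high-Vt group is relevant to the 14-16 arm, which Section 6 supports but does not prove, and that controls in Section 9 has the meaning used elsewhere in the protocol.

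No endpoint, estimate or analysis changes. This should be fixed because it bears on disclosure and safety oversight and costs little, but it does not threaten the trial's validity.

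**What to change.** 1. Reconcile the risk statement in Section 2 with Sections 1, 6 and 8 and with Hypothesis 1. State what the evidence suggests about pulmonary outcomes at each assigned range, say that it is preliminary and largely observational, give the overlap with usual practice and its limits (including the differing accounts of PEEP), and say that assignment is by chance. No ventilator setting needs to change for this.
2. Check that the ventilated-group consent form agrees with the revised text.
3. At the existing 50% review, tabulate every pulmonary event listed in Section 9, related or not, by coded Vt arm, in addition to the comparison with non-ventilated controls and the pneumonia criterion. Coded labels keep the arm identities from the blinded investigator and statistician. With about 7 or 8 participants per arm, the table is descriptive.

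The cost is an ethics-board amendment, one extra table at a review already planned, and a possible small loss in consent rate.

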3. STUDY POPULATION

Sample Size: We plan to recruit 45 subjects (15 in low Vt, 15 in high Vt, and 15 in the control group). We will recruit 30 adults with acute cervical SCI admitted on mechanical ventilation from TIRR MHH and Craig Hospital and an additional 15 people with acute cervical SCI not dependent on mechanical ventilation at admission to serve as controls from TIRR MHH.

Criteria for Recruitment: All consecutive patients with SCI admitted to TIRR MHH and Craig Hospital will be screened for eligibility based on inclusion and exclusion criteria during the study period. The screening will involve the review of history from the patient or primary admitting clinician. If a patient meets eligibility criteria, the research coordinator will provide further information on the study, answer any questions, and recruit if they are willing to participate and provide consent.

Inclusion Criteria: Subjects must meet all of the inclusion criteria listed below to participate in this study.

- Adult patients \geq 18 years (Lung volumes and ventilator settings are different for ages <18 years).
- Acute SCI of duration \leq four months
- Mechanical ventilation subjects: traumatic or non-traumatic cervical SCI with neurological level C1-C5 admitted to our acute inpatient rehabilitation facility (AIR) on mechanical ventilation.
- Control subjects: traumatic cervical SCI admitted to our acute inpatient rehabilitation facility (AIR) who are not dependent on mechanical ventilation.

Exclusion Criteria: All subjects meeting any of the exclusion criteria listed below at baseline will be excluded from participation.

- Severe dysphagia due to concomitant brain stem injury, which increases the risk of pneumonia
- Severe brain injury resulting in dysphagia and inability to follow instructions to perform vital capacity measurements
- ARDS or severe lung disease (required supplemental oxygen or ventilator prior to SCI) at the time of admission (these conditions will not allow patients to randomize because target Vt may below)
- Prolonged antibiotics for > 3 weeks at the time of admission due to infection (e.g., osteomyelitis, epidural abscess, etc.),
- Presence of diaphragmatic pacemaker.

Withdrawal Criteria: Possible reasons for discontinuation of study intervention: Intolerance to proposed ventilator settings.

Subject Replacement: Subjects who drop out will be replaced by screening the inpatient unit. Subjects that drop out will be followed for secondary outcomes collected via the EMR while they remain at TIRR.

4. TRIAL SCHEDULE:

Participants will be enrolled in the study upon consent within 48-72 hrs of admission to TIRR MHH or Craig Hospital, and participation will end on discharge from respective hospital. The trial will start upon IRB and respective hospital approval on July 1, 2021, and end on June 30, 2024.

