AEs and Reportable Events will be recorded. AE will be recorded on the appropriate case report form (CRF) page from the time written informed consent is obtained until completion of the study or until resolution of the reportable event. Information to be collected includes the description of the AE, date and time of onset, severity, duration, causality, outcome, and relationship to the study procedure. If an AE is assessed by the I

UTHealth
Houston

IRB NUMBER: HSC-MS-21-0222
as not reasonably
IRB APPROVAL DATE: 02/23/2023

attributable to study intervention, its occurrence must also be recorded in the source documents and reported on the CRF.

Safety Monitoring Plan

The Data Safety Monitoring Plan (DSMP) for the research study includes statistical analysis on rates of morbidity of study participants compared to controls by the PI and the statistician at 50% recruitment stage. If preliminary results suggest the risk of pneumonia is <25% in one group compared to another group, we will stop the study.

We will follow standard clinical procedures in the event of a desaturation episode. The most common cause of desaturation is a mucus plug in people with spinal cord injury in the rehabilitation setting. We will first suction the patient. If a patient is still not improving with suctioning, we will adjust ventilator settings, including tidal volume, to address clinical needs. Given that we have a range of VT in each group, we will first adjust within that range if VT has to be adjusted. If a person requires further adjustment in VT, we will allow the changes in ventilator settings to meet the patient's needs. We will not remove any patient from the study. We will include this data for intent to treat analysis. However, this event will be considered a treatment failure, and data will be included to calculate feasibility metrics for a larger study.

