11. SAMPLE SIZE AND STATISTICAL METHODS

Determination of Sample Size:

The purpose of the proposed pilot trial is to test the feasibility of conducting a randomized control trial comparing high vs. low Vt MV. Given the complexity of this study and practice variation, it is essential to evaluate recruitment and study procedures. Our cohort study data suggest that approximately 19 patients per year will meet eligibility. Based on Fenton et al. study comparing high vs. low Vt MV in SCI, we anticipate a total recruitment rate of 80% (i.e., that 80% of the eligible would consent for the study), i.e., on average, we are expecting to enroll at least 10-12 participants with SCI who are on mechanical ventilation per year for mechanical ventilation group and total of 30 subjects for 3 years.

For the control group, we will recruit cervical SCI (neurological level C1-C5) who are not dependent on mechanical ventilation at admission to our acute inpatients rehabilitation facility. We plan to recruit a total of 15 subjects in 2 years. This is a pilot study based on feasibility of completing study within the above time frame this sample size was determined. We will have atleast 15 subjects in each group for the analysis.

Statistical and Analytical Plans:

Baseline data and unadjusted analysis of outcome variables will be presented as mean with standard deviation (SD) for a continuous variable with normal distribution otherwise as median with interquartile range (IQR). Categorical and ordinal data will be reported as totals and frequencies for baseline data and unadjusted analysis of outcome variables.

Aim 1: Respiratory outcomes: We will report relative risk with credible interval and posterior probability. We will use neutral prior, and for binary outcomes, this will be centered at RR of 1 with 95% credible interval of 0.3 to 3. Bayesian inference combines a prior or an estimated effect distribution based on previous studies and likelihood, which summarizes findings from the present study.³⁵ All Bayesian analyses will use similar models as the frequentist analyses. We will report risk ratios with 95% credible intervals and posterior probability of benefit or harm associated with the intervention.

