12. ETHICAL CONSIDERATIONS

Informed Consent

Subjects will be recruited upon admission, meeting the established I/E criteria, and consenting to participation. Informed consent will be obtained by the PI and/or the research assistant, and they will have one day to decide. All procedures will be fully disclosed, and we will give the subjects as much information as possible about the intervention and the data analysis. The subjects will be given the opportunity to ask questions. They will be reassured that their participation in this study is voluntary, and they have the right to withdraw at any time from the study. Any new findings developed during the course of this research that may affect their willingness to continue will be provided to subjects. Choosing not to participate or withdrawing from this study will not negatively affect subjects' right to any present or future medical treatment or employment to which the subjects are otherwise entitled. Although the PI and collaborators may have admitting privileges, they do not have an inpatient service, minimizing unperceived coercion, which may be possible if the admitting physicians were directly involved in the study. Besides, the subjects will be asked to sign a Research Subject Authorization Confidentiality and Privacy Rights form to comply with HIPAA regulations.

IRB review

This protocol and the associated informed consent documents have been submitted to the IRB for review and approval.

Confidentiality of Data and Patient Records

All patient records will remain confidential. Data with Protected Health Information (PHI) will be de-identified and given a subject ID found on the Linking Log. The Linking Log is a separate file in a separate folder found on the PI's desktop computer.

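### Replacement of dropouts and a pneumonia count that starts only after target Vt leave the primary comparison short of all randomised patients counted from a common start

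*Combined protocol and SAP*

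**What the plan says.** All references are to the combined protocol and SAP.

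- **Section 3, Subject Replacement:** "Subjects who drop out will be replaced by screening the inpatient unit". The next sentence reads "Subjects that drop out will be followed for secondary outcomes collected via the EMR while they remain at TIRR". Dropout is not defined, and replacement is not confined to patients who leave before randomisation.
- **Section 3, Withdrawal Criteria:** "Possible reasons for discontinuation of study intervention: Intolerance to proposed ventilator settings". No other reason is given.
- **Section 4, Trial Schedule:** "participation will end on discharge from respective hospital", so both hospitals are in view there. Section 3 recruits ventilated patients at both.
- **Section 6, Outcomes:** pneumonia is the primary outcome. The outcomes labelled secondary are the feasibility measures. A pneumonia episode counts only if it develops 48 hours after target Vt is reached.
- **Section 9, Safety Monitoring Plan,** in the paragraph on desaturation and Vt adjustment: "We will not remove any patient from the study. We will include this data for intent to treat analysis". It adds that "this event will be considered a treatment failure, and data will be included to calculate feasibility metrics for a larger study".
- **Section 11:** "We will have atleast 15 subjects in each group for the analysis". The Aim 1 analysis is described without an analysis set or a rule for dropouts.
- **Section 12:** subjects are told that "they have the right to withdraw at any time from the study".

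**The concern.** Two stated rules can separate the primary analysis from the randomised comparison.

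The first is replacement. If a randomised patient leaves because the assigned settings are not tolerated, and intolerance depends on the arm, substituting another patient makes the analysed group a selected one. The promise of 15 per group for analysis can be met by such substitution.

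The second is the counting start. Reaching target Vt happens after randomisation, and the two arms have different distances to travel. Pneumonia in the first days after randomisation can then count in one arm and not in the other. For a patient who never reaches target, counting never begins.

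At stake is Hypothesis 1, which looks for more than 70% posterior probability that lower Vt carries a lower pneumonia risk. With about 15 patients per arm, a few patients or events matter.

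**Working it through.** **1. Planned numbers.** Section 11 expects 10 to 12 ventilated patients a year: 10 × 3 = 30, or 15 per arm, which reproduces the stated total (12 × 3 would give 36). Section 6 expects 80% retention. If every non-retained patient were a dropout (an assumption), that is 0.20 × 15 = 3 per arm.

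**2. One patient under the two rules.** Take a randomised patient who cannot tolerate the assigned range.
- Under section 3, intolerance is listed as a withdrawal criterion. If that makes the patient a dropout, the patient is replaced and followed for secondary outcomes at one hospital.
- Under section 9, the patient is not removed, enters an intent-to-treat analysis and counts as a treatment failure.
- Section 11 does not choose between them.

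The rules fit together if dropping out means leaving the study under the right described in section 12. No passage says so. Even then, a randomised patient may be replaced, and follow-up for pneumonia is not stated.

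**3. When counting starts.** Inputs: admission median 7.5 ml/kg (section 8); increase of 50 to 100 ml per day (section 6, Intervention); lower target edges of 14 and 8 ml/kg. Predicted body weight (pbw) of 50 to 70 kg is my assumption.

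Days to target = (target − 7.5) × pbw ÷ daily increase.
- High arm: 6.5 × 50 = 325 ml and 6.5 × 70 = 455 ml; 325/100 = 3.25 days to 455/50 = 9.1 days.
- Low arm: 0.5 × 50 = 25 ml and 0.5 × 70 = 35 ml; 25/100 = 0.25 day to 35/50 = 0.7 day.
- Gap at the same pbw and rate: 6 × pbw ÷ rate, from 300/100 = 3.0 days to 420/50 = 8.4 days.

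The added 48 hours is common to both arms and leaves the gap unchanged. The section 6 schedule allots Day 1-4 to titration, which matches only the faster end of the high-arm range. Those two statements need to be reconciled.

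**4. What replaced patients could do to the result.** The documents give no pneumonia rates, so the counts are assumed. With a/n₁ events in the low arm and b/n₂ in the high arm:
- L = ln(RR), v = 1/a − 1/n₁ + 1/b − 1/n₂
- prior mean 0, SD s = ln(3)/1.96 = 0.561 (section 11 prior)
- posterior mean m = L(1/v)/(1/v + 1/s²), posterior SD = (1/v + 1/s²)^(−1/2)
- P(RR<1) = Φ(−m/SD)

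Fifteen per arm are analysed after replacement; k replaced patients per arm are then added back, with 0 to k events in each arm. Cells show the range of P and how many combinations move to the other side of 70%.

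| Analysed, low vs high | P | k=1 | k=2 | k=3 |
|---|---|---|---|---|
| 6/15 vs 9/15 | 0.81 | 0.72–0.87; 0 of 4 | 0.61–0.91; 1 of 9 | 0.50–0.94; 3 of 16 |
| 6/15 vs 6/15 | 0.50 | 0.39–0.61; 0 of 4 | 0.29–0.71; 1 of 9 | 0.21–0.79; 3 of 16 |
| 4/15 vs 6/15 | 0.71 | 0.61–0.79; 1 of 4 | not needed | not needed |

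The crossing in the third row:
- 4/15 vs 6/15: L = −0.405, v = 0.283, m = −0.213, SD = 0.386, P = 0.71.
- Add one low-arm dropout with pneumonia and one high-arm dropout without. 5/16 vs 6/16: L = −0.182, v = 0.242, m = −0.103, SD = 0.370, P = 0.61.

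Taking the prior SD from both ends of the stated interval, (ln 3 − ln 0.3)/(2 × 1.96) = 0.587, leaves every crossing count in the table unchanged. These are counts of combinations, not probabilities.

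**The case against.** The strongest reply is that the plan already retains these patients. Section 9 covers the case most open to bias, a patient who needs Vt outside the range, and puts that patient into intent to treat. Section 3 speaks of stopping the intervention, not leaving the study. Section 6 collects outcome data and adverse events from the medical record to discharge, section 7 covers the records of both hospitals, and section 9 lists pneumonia as an adverse event. The formal secondary outcomes are feasibility rates, so the follow-up sentence may be loosely worded and mean clinical data generally.

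Much of this stands. A reader might infer that the plan excludes dropouts from the primary analysis; no passage says that, and most pneumonia would probably be captured. What remains is that having the data does not decide who is analysed. The intent-to-treat sentence is tied to Vt adjustment and sits beside an unrestricted replacement rule.

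A reader might also infer that replaced patients fall out of the adherence and retention denominators. The documents do not support that: Hypothesis 2 in section 2 refers to recruited subjects and section 6 to those enrolled, and a replaced patient is both. Section 11 also plans a CONSORT account of dropout.

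On the counting start, waiting until the assigned exposure is in place has a clinical rationale, and the Day 1-4 schedule suggests a smaller gap than the slow end of my range. Neither makes the start the same in both arms.

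**Conclusion.** The point holds in limited form and should be fixed. As written, the plan permits a randomised patient to be replaced without stated follow-up for the primary outcome, and leaves open whether a patient who stops for intolerance stays in the pneumonia comparison. It also starts counting at an event after randomisation that the arms reach at different times: about 3.3 to 9.1 days against under 1 day, given the median starting Vt and an assumed pbw of 50 to 70 kg.

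Taken alone, the later start shortens the counted period in the high arm. The size and direction of the net bias cannot be derived, because the documents give no pneumonia or dropout rates by arm.

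Neither general claim about the 70% line is supported. One dropout per arm does not cross it with 6/15 vs 9/15 or 6/15 vs 6/15, but can with 4/15 vs 6/15 (P from 0.71 to 0.61). All these counts are assumed.

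**What to change.** - Reconcile the withdrawal and replacement text in section 3 with the Safety Monitoring Plan in section 9, and define dropout.
- State in section 11 that every randomised ventilated patient at both hospitals is followed in the medical record for pneumonia to discharge, unless consent for data use is withdrawn, and is analysed in the assigned arm. Count any replacement as an additional patient, not a substitute.
- For the primary analysis, start pneumonia counting at a point anchored to randomisation and identical in both arms, with the interval chosen by the study team. This also covers patients who never reach target. Keep the count from 48 hours after target as a sensitivity analysis.

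The cost is a wording amendment and slightly more analysis work, since record-based outcomes to discharge are already planned. There are two downsides. Some early episodes unrelated to the assigned Vt will be counted. Withdrawal of consent for data use may leave fewer than 15 per arm unless additional patients are enrolled.
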